#### Secondary safety endpoints:

The following safety parameters will be evaluated for the duration of the study:

- Type, frequency, severity, and relationship of AEs to investigational product (IP).
- Number of patients who discontinue IP due to any AE.
- Frequency of clinically significant changes in vital signs and/or laboratory findings.

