### 5.5 Rescue Medication and Risk Management Plans

Cautions from the manufacturer of Ifenprodil include monitoring for hypotension, palpitations/increased heart rate, and risk of bleeding (including those patients on drugs with a risk of bleeding). Investigators should monitor their patients for occurrence of these adverse events and proceed as follows:

Vasopressin can be used as a rescue therapy for patients who suffer vasodilative shock. If low blood pressure occurs, use of vasopressor medication may also be considered. This may or may be coincident with an increased heart rate, in which case a vasopressor may correct both events. In the event of an increased heart rate in the absence of coincident hypotension, use of a positive inotropic agent may be considered. In the event of an increased risk of bleeding, antifibrinolytic therapy may be considered. Please consult with the Medical Monitor regarding the best course of treatment should any of these events occur.

In addition, patients should be monitored for elevation in liver enzymes. Those patients whose ALT/AST rise to  $>5x$  the upper limit of normal and/or Child Pugh score of 10-15 should be discontinued from study medication (ifenprodil). In addition, the Medical Monitor and DSMB will monitor for the occurrence of these adverse events as part of their normal safety review. Additional guidance or updates to the protocol will be provided if necessary.

The DSMB will review the adverse events profile after 25, 50, 75 and 100 patients enrolled in the study, then every 50 patients thereafter. Particular attention will also be paid to patients over 65 for the frequency and severity of serious adverse events (e.g. ALT/AST, creatinine) as the manufacturer has mentioned caution should be taken in this particular age group. If, based on the DSMB's opinion, there is a significant concern in any of the identified risk groups, additional restrictions may be added to the inclusion/exclusion criteria.

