### **10.10 Safety Analysis**

Safety and tolerability will be assessed by AEs, laboratory testing (haematology, biochemistry, and urinalysis), and vital signs.

The safety analyses will be performed using the safety population ([Section 10.2](#)). Treatment-emergent AEs will be classified using the Medical Dictionary for Regulatory Activities (MedDRA) classification system. All TEAEs will be summarized by system organ class, preferred term, severity, and relationship to IP. Treatment Emergent Adverse events leading to death or to discontinuation from treatment and TESAEs will also be tabulated. All adverse events, regardless of whether it is treatment emergent or not, will be listed.

Laboratory data will be summarized descriptively by visit. In addition, shift tables showing the number of patients with values low, normal, and high compared to the normal ranges pre-treatment versus post-treatment will be provided for the applicable lab parameters. Change from baseline analysis will also be reported if applicable. All laboratory data will be listed.

Vital sign measurements, including weight, will be summarized descriptively by visit and presented as shift tables and listed.

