Demographics/Medical History	•				
Physical Exam	•				
Vital signs ^c	•	•	•	•	
Clinical support data collection ^f	•	•	•	•	
Safety Laboratory Testing ^d	•	•	•	•	
Cytokine Markers ^k	•	•	•		
Child-Pugh Score ⁱ	•	•			
PaO2 and PaO2/FiO2 ratio ^j	•	•	•	•	
ECG	•				
Cough Severity (VAS) ^e	•	•	•	•	
Extent of Dyspnea (Likert Scale) ^e	•	•	•	•	
Adverse Events documented	•	•	•	•	•
Concomitant Medications	•	•	•	•	
Randomization	•				
Administer IP	•	•			
Vital Status					• ^g

^a Screening/baseline may occur up to 24 hours prior to randomization

^b Treatment can be given up to 14 days post randomization, or until hospital discharge, whichever comes first. If patient is discharged prior to Day 14, the next visit should be Visit 2.

^c Includes blood pressure (measured after the patient has been in a seated position (if possible) for ≥3 minutes of rest), pulse, respiratory rate, body temperature, and SpO2. Body weight and height will be measured at the screening visit only.

^d Baseline, Days 3, 5, 8, 11 if hospitalized, Day 15, Day 29

^e Baseline, Days 2, 4, 8, and 14 if hospitalized, Day 15 (if not done Day 14), Day 29

^f Includes NEW Score, on Baseline, Days 3, 5, 8, 11 if hospitalized, Day 15, Day 29

^g Vital status (is patient alive)

^h Baseline, Days 5 (or discharge, whichever comes first) and 15. Day 29 for patients with viral RNA detected at Day 15. Qualitative (mandatory) and Quantitative (if available) testing done all days.

ⁱ Baseline, Days 3, 5, 8, 11 if hospitalized

^j Minimum complete baseline, Days 3, 5, 8, 11, 15 and 29. If PaO2 not able to be taken, SpO2 should be obtained using a forehead sensor. Fingertip probes may be used if forehead sensors are not available. Remain consistent with the method of testing for the patient over the course of the study.

^k Cytokine markers at Baseline, Day 5, Day 15 (if available per local lab): IFN- γ , GM-CSF, IL-6, IL-12, TNF- α

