3.1 General Considerations

All data collected on the electronic case report form (eCRF) will be presented in the data listings and will be listed and sorted by treatment arm, participant number and visit, where applicable. All descriptive summaries will be presented by treatment group and scheduled visit/time point (where applicable).

Unless otherwise stated, the following methods will be applied:

- **Continuous variables:** Descriptive statistics will include the number of non-missing values (n), arithmetic mean, standard deviation (SD), median, minimum and maximum values.

The minimum and maximum values will be displayed to the same decimal precision as the source data, the arithmetic mean, SD and median values and other derived values will be displayed to one more decimal than the source data for the specific variable.

95% Confidence Intervals (CIs), mean differences (among treatments and from baseline) and adjusted means values will be displayed to one more decimal than the source data for a specific variable. P-values will be displayed to 3 decimal places.

The appropriate precision for derived variables will be determined based on the precision of the data on which the derivations are based, and statistics will be presented in accordance with the aforementioned rules.

- **Categorical variables:** Descriptive statistics will include counts and percentages per category. The denominator in all percentage calculations will be the number of participants in the relevant analysis population with non-missing data, unless specifically stated otherwise. Percentages will be displayed to one decimal place. Proportions will be displayed to 3 decimal places.

95% Confidence Intervals (CIs), difference in proportions, odds ratio's and other categorical parameters will be displayed to one decimal place for percentages. Proportions will be displayed to 3 decimal places. P-values will be displayed to 3 decimal places.

- **Repeat/unscheduled assessments:** Only values collected at scheduled study visits/time points will be presented in summary tables. If a repeat assessment was performed, the result from the original assessment will be presented as the result at the specific visit/time point. All collected data will be included in the data listings.
- **Assessment windows:** All assessments will be included in the data listings and no visit windows will be applied to exclude assessments that were performed outside of the protocol specified procedure windows.

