12.4 Vital Signs

The following vital signs measurements will be taken at the time points specified in the study procedure schedule (section [Table 1](#)):

- Systolic blood pressure (SBP) (mmHg)
- Diastolic blood pressure (DBP) (mmHg)
- Pulse Rate (beats/min)
- Respiratory rate (breaths/min)
- Body Temperature ($^{\circ}$ C)
- Oxygen Saturation SpO₂ (%)
- Level of Consciousness (Alert, Arousable only to voice, Arousable only to pain, Unresponsive)
- Presence of clinically significant result

Summary statistics for vital sign parameters in accordance to [section 3.1](#) will be presented for baseline and for each scheduled pre and post-baseline visit (which also includes change from baseline, clinical significance) where applicable. These summary tables will be done for Safety population for treatment groups defined in [section 3.4](#).

The listing of vital sign parameters will include all the information collected. In addition, the observations that are used as the baseline record (value) for each parameter will be flagged, and the change from baseline values at each pre and post baseline (scheduled and unscheduled) visit will be presented along with whether the result was clinically significant (AE/MH numbers if applicable) and reasons not done. This listing will be presented by treatment arm (grouping provided in [section 3.4](#)) sorted by patient ID and visit for the Safety population, along with the age and sex and baseline weight of the patient.

12.5 12-Lead Electrocardiogram (ECG)

The following ECG measurements will be taken at the time points specified in the study procedure schedule (section [Table 1](#)):

- Ventricular HR (beats/min)
- PR interval (msec)
- QRS interval (msec)
- ST segment (msec)
- QTcF interval (msec)
- Presence of clinically significant result (normal, abnormal not clinically significant, abnormal and clinically significant)

Summary statistics for 12-Lead ECG parameters in accordance to [section 3.1](#) will be presented for baseline and for each scheduled pre and post-baseline visit (which also includes change from baseline). These summary tables will be done for Safety population for treatment groups defined in [section 3.4](#)

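### SAP 12.4 omits the protocol's vital-sign shift tables and has no per-patient worst-value summary of blood pressure or pulse, so the number of patients affected rests on open-label AE reporting

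*SAP*

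**What the plan says.** **Why these signs matter.** Protocol 5.5 states: "Cautions from the manufacturer of Ifenprodil include monitoring for hypotension, palpitations/increased heart rate, and risk of bleeding". Hypotension and tachycardia are in exclusion criterion 1, and vasodilative shock is among the discontinuation criteria in Protocol 5.4.2. A safety endpoint in Protocol 3.2, repeated in SAP 2.4, is "Frequency of clinically significant changes in vital signs and/or laboratory findings".

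**What is measured.** Blood pressure and pulse are scheduled at Visit 1, daily on Days 2 to 14 while in hospital, and on Days 15 and 29. The ECG is scheduled at Visit 1 only.

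**What the protocol plans.** Protocol 10.10: "Vital sign measurements, including weight, will be summarized descriptively by visit and presented as shift tables and listed".

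**What the SAP plans.** SAP 12.4 lists the vital signs and the item "Presence of clinically significant result". Summary statistics "will be presented for baseline and for each scheduled pre and post-baseline visit (which also includes change from baseline, clinical significance) where applicable". A listing shows all scheduled and unscheduled values. Under SAP 3.1, continuous variables get n plus "arithmetic mean, standard deviation (SD), median, minimum and maximum values", and "Only values collected at scheduled study visits/time points will be presented in summary tables".

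**The adverse-event route.** Protocol 7.4.1 has clinically significant abnormal vital signs reported as AEs. SAP 12.2 tabulates treatment-emergent AEs by preferred term and arm, counting each patient once per event.

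**The concern.** The endpoint is a frequency, and the natural unit is the patient: how many in each arm had low pressure or a fast pulse while on study. SAP 12.4 works visit by visit and never summarises over visits. The one element of the protocol's plan that classifies readings against baseline, the shift table, does not appear in it.

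What remains for counting patients is the AE route. It requires an investigator to judge a reading clinically significant, knowing the arm (Protocol 4.4 says that patients, investigators and site staff are aware of treatment in Phase 2b). Protocol 8.1 also excludes abnormal findings associated with the underlying disease unless they are more severe than expected. In hospitalised COVID-19 patients, low pressure or a fast pulse can often be put down to the disease, and that attribution too is made knowing the arm. At stake is whether the comparison of two doses with SOC on the drug's named cautions can be checked against the measurements before Phase 3 is designed.

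**Working it through.** The documents give no figure on this point, so there is none to reproduce. The check is a comparison of texts, followed by a short illustration.

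**1. Protocol against SAP**

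| Item | Protocol 10.10 | SAP |
|---|---|---|
| Vital signs by visit | Yes | Yes (12.4) |
| Vital-sign shift tables | Yes | Not named (12.4) |
| Laboratory shift from baseline | Yes | Yes (12.3) |
| Declared in SAP 13 as a change | – | No; only the remdesivir ad-hoc analysis is listed |
| Patients affected at any time, or worst value | Not named | Not named |

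SAP 12.3 keeps the shift from baseline for laboratory data, so the silence in 12.4 is specific to vital signs.

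Restoring the protocol's wording would not be enough. Protocol 10.10 does not say how the shift is defined, neither document gives low and high limits for blood pressure or pulse, and a shift table at each visit is still not a count of patients ever affected. The protocol's inclusion of weight cannot be carried out either: "Body weight and height will be measured at the screening visit only".

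**2. Can by-visit flags give patients affected?**

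Assume a share p of an arm is flagged at each of the 13 daily visits (Days 2 to 14), with everyone still in hospital.

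- Same patients every day: share ever flagged = p.
- Independent days: share ever flagged = 1 − (1 − p)^13.

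| p per visit | Same patients | Independent days |
|---|---|---|
| 1% | 1% | 1 − 0.99^13 = 12.2% |
| 2% | 2% | 1 − 0.98^13 = 23.1% |
| 5% | 5% | 1 − 0.95^13 = 48.7% |

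With 50 patients per arm, 2% is one patient per visit. The by-visit table would look the same whether one patient was flagged 13 times (1/50 = 2%) or 13 patients once each (13/50 = 26%).

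**3. Can the means or extremes give it?**

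If k of 50 patients have a systolic fall of d mmHg at a visit, that visit's mean moves by k × d / 50. For assumed falls of 20 to 40 mmHg:

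- k = 1: 20/50 to 40/50 = 0.4 to 0.8 mmHg.
- k = 5: 100/50 to 200/50 = 2 to 4 mmHg.

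The mean moves little. The visit minimum would show an extreme reading, but not how many patients had one.

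**4. Which readings enter the tables?**

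Unscheduled readings stay out of the summary tables, so a reading prompted by an episode between scheduled checks appears only in the listing.

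**The case against.** The strongest reply is that episodes judged clinically significant are already counted per patient and by arm as treatment-emergent AEs, and that the SAP 12.4 listing links flagged readings to AE numbers. There is more: each visit's minimum and maximum are tabulated; action taken with ifenprodil and AEs leading to discontinuation or death are summarised (SAP 12.2); concomitant medication given for AEs is summarised (SAP 9); and the Medical Monitor and DSMB watch these cautions (Protocol 5.5). The pilot is described as essentially exploratory (SAP 11.1).

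All of that stands, and it rules out two stronger readings.

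- A reader might infer that hypotensive episodes are averaged away and go uncounted per patient. The documents do not support this: the AE tables count them once judged clinically significant and reported, and the by-visit extremes and flags remain visible.
- A reader might also argue that a per-patient count would detect a difference with much better power. No such claim can be made. The SAP plans no test on vital signs, and the documents give no rate for hypotension. The nearest figure, in Protocol 8.4, places heart palpitations among side effects seen in 0.1 to 5% of patients.

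The layouts are in mock shells cited in SAP section 16 and not available here. A shift table planned only there cannot be ruled out, so the SAP text shows an omission, not a deliberate removal.

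The reply does not remove the dependence on arm-aware judgement or the exemption for disease-associated findings. The other AE-based summaries share both limits.

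**Conclusion.** The point holds as a discrepancy between protocol and SAP plus a reporting gap. The vital-sign shift tables of Protocol 10.10 are missing from SAP 12.4 and not declared in section 13. No table planned in the SAP text gives, from the measurements, the number of patients with low pressure or a fast pulse at any time. That frequency rests on investigator-reported AEs.

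The gap cannot be sized as a bias, because the documents give no rate of under-reporting. It can be sized as lost information: the same by-visit flags fit a per-patient share of 2% or 23% in the example above, which assumes 13 daily visits with nobody discharged. Discharge makes the by-visit tables harder to combine, since daily readings are taken only in hospital.

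This is a cheap improvement to safety reporting. The primary analysis is not affected.

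**What to change.** In SAP 12.4:

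1. **Restore the shift tables** of Protocol 10.10, or declare and justify their omission in section 13. Define the categories. The NEWS bands of Protocol Appendix 16.1 serve for systolic pressure and heart rate; diastolic pressure has no NEWS band and needs its own statement. Say that weight is excluded because it is measured once.
2. **Add a by-arm table** of the number and percentage of patients whose worst scheduled post-baseline reading through Day 15 falls in each NEWS band, taking worst as the lowest systolic pressure and the highest heart rate. Give Newcombe 95% CIs for each dose against SOC, and summarise each patient's lowest systolic pressure and highest pulse. The bands are reporting categories only, not rules for managing patients.
3. **Include SOC patients explicitly.** SAP 4.1.3 defines the Safety population by receipt of study drug, which read literally leaves SOC out of the comparison.
4. **Show unscheduled readings only in a sensitivity version**, because patients on drug may be measured more often when investigators are asked to watch for these cautions.
5. **Repeat the table for Days 1 to 5** (in effect the readings of Days 2 to 5, as Day 1 is baseline), because length of stay differs. In the planning distribution of SAP Table 2, 36 + 37 = 73% of SOC and 31.90 + 50.70 = 82.6% of treated patients are out of hospital at Day 15, so the arms could differ in readings per patient.

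The cost is one or two extra tables from data already collected. The drawback is that any-time counts depend on the number of readings, which items 4 and 5 expose but do not remove. Scheduled readings will also miss short episodes between checks, so the table supplements the AE tables and does not replace them.

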12.6 Physical Examinations

By-participant data listings will be created for all physical examination parameters and all time points by treatment arm (grouping provided in [section 3.4](#)) along descriptions of abnormality, associated AE/MH numbers where applicable, and reasons not done, sorted by patient ID and visit for the Safety population, along with the age and sex and baseline weight of the patient.

12.7 Pregnancy Test Results

All information related to pregnancy testing (whether urine and serum based, result, reasons not done, date and time of sample collection) will be presented in the by-participant data listings by treatment arm (grouping provided in [section 3.4](#)) sorted by patient ID and visit for the Safety population, along with the age and sex and baseline weight of the patient.

12.8 Child Pugh Score

Summary statistics for total Child Pugh score in accordance to [section 3.1](#) will be presented for baseline and for each scheduled pre and post-baseline visit (which also includes change from baseline, clinical significance) where applicable. These summary tables will be done for Safety population for treatment groups defined in [section 3.4](#)

All information related to child Pugh score (component of child Pugh score, total child Pugh score, result, reasons not done, date and time of sample collection) will be presented in the by-participant data listings by treatment arm (grouping provided in [section 3.4](#)) sorted by patient ID and visit for the Safety population, along with the age and sex and baseline weight of the patient.

13. CHANGES TO THE PLANNED ANALYSIS

14. AN AD-HOC ANALYSIS BASED ON ALL PATIENTS WHO RECEIVED REMDESIVIR AS PART OF THEIR SOC IN ALL TREATMENT ARMS MAY BE PERFORMED AS DESCRIBED IN 14.3.

INTERIM AND FINAL ANALYSIS

14.1 Interim Analyses

The DSMB will review safety data after every 25 patients are entered into the trial up to 100 patients, and then at every 50 patients. Ad hoc reviews will be undertaken if there are other specific safety concerns. The study will not stop enrolment awaiting these DSMB reviews, though the DSMB may recommend temporary or permanent cessation of enrolment based on their safety reviews. Based on the recommendations of the WHO R&D Blueprint Clinical Trials Expert Group and given the severity of illness in COVID-19, there are no pre-specified study stopping rules for safety.

For Phase 2b, an interim analysis will also be performed when 75 patients completed Day 15 assessments for primary endpoint. For this interim analysis with first 75 patients with Day 15 efficacy data, in addition to standard DSMB outputs, the following descriptive statistics efficacy analysis will also be presented:

1. WHO-7 efficacy with Day 15 assessment
2. Status on an ordinal scale assessed daily while hospitalized and on days 15
3. NEWS assessed days 3, 5, 8, 11 while hospitalized and on days 15 in IP versus control group patients
4. Effect on the rate of change of partial pressure of oxygen (PaO₂) and PaO₂/FiO₂ ratio taken at baseline and measured once daily up to 2 weeks of treatment in IP versus control group patients
5. Rate of mechanical ventilation in IP versus control group patients (Patients who received Invasive/non-invasive Mechanical Ventilation by Day 15)

For item 5, if a patient did not experience mechanical ventilation by Day 15, he/she will be marked as a negative response even if the patient did experience mechanical ventilation past Day 15. This is different to the final analysis described above.

A preliminary full analysis report of 150 patients with up to Day 29 data entered may also be presented.

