11.6 Secondary Efficacy Analysis: Respiratory Support

For the part of the analysis, respiratory support is defined as:

- Any respiratory support (any of Oxygenation only, Mechanical Ventilation (Invasive and non invasive), ECMO)
- Oxygenation only
- Invasive Mechanical Ventilation
- Non Invasive Mechanical Ventilation
- ECMO

11.6.1 Rate of Respiratory Support: Oxygenation only, Mechanical Ventilation (Invasive and non invasive), ECMO

Counts and percentages of patients for respiratory support at least once will be reported for each treatment arm. If patients were eligible for respiratory support but did not receive one due to lack of resources, an additional analysis on counts and percentages of patients required to receive respiratory support will be reported for each treatment arm. Separate 95% CIs (Newcombe) and p-values (Chi-Squared test without continuity correction) will be computed between SOC and treatment arms A and B for patients with at least one respiratory support.

11.6.2 Duration of Respiratory Support: Oxygenation only, Mechanical Ventilation (Invasive and non invasive), ECMO

Counts and percentages of patients with the following categories (based on total number of hours of respiratory support) will be reported for each type of respiratory support and for each treatment arm. The duration calculation is only applicable to patient with respiratory support. For patients with ongoing respiratory support with no end date and time at data cut off, the date of data cut off will be used to calculate the end date for the ongoing at time of data cut off category.

The duration is defined as:

Date and time at end of respiratory support-Date and time at end of respiratory support.

- < 6 hours
- \geq 6 hours but < 12 hours
- \geq 12 hours but < 24 hours
- \geq 24 hours but < 72 hours
- \geq 72 hours but < 120 hours
- > 120 hours
- Ongoing at time of data cut off (\geq 6 hours) [The hour can be amended based on real data]
- Ongoing at time of data cut off (\geq 12 hours) [The hour can be amended based on real data]
- Ongoing at time of data cut off (\geq XX hours) etc...
- Prolonged respiratory support (consecutive respiratory support for 21 days with at least \geq 6 hours per day)

Separate 95% CIs (Newcombe) and p-values (Chi-Squared test without continuity correction) will be computed between SOC and treatment arms A and B for prolonged respiratory support.

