11.6.3 Time to Respiratory Support: Oxygenation only, Mechanical Ventilation (Invasive and non invasive), ECMO

The time to respiratory support (Day) is defined as:

Date of first respiratory support – Date of Baseline Assessment + 1.

If the patient did not require respiratory support, the patient will be censored at the last known date the patient is known to not require respiratory support:

Final Date of Confirmation of no respiratory support needed - Date of Baseline Assessment + 1.

If a patient died before obtaining respirator support, the patient will be censored as a competing risk based on the following:

Date of Death - Date of Baseline Assessment + 1.

11.6.4 Time from first Oxygenation Support to first termination of Oxygenation Support:

This calculation is only applicable for those with oxygenation support.

The time to from first oxygenation support to first termination of oxygenation support is defined as:

Date of first termination of oxygenation support – Date of first oxygenation support + 1.

If the patient was still on oxygenation support, the patient will be censored at the last known date the patient is known to still on oxygenation support:

Final date of confirmation of still on oxygenation support - Date of first oxygenation support + 1.

If a patient died before terminating oxygenation support, the patient will be censored as a competing risk based on the following:

Date of Death - Date of Baseline Assessment + 1.

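### The ventilation rate counts a patient who dies unventilated as a non-event; a ventilated-or-died comparison should be pre-specified beside it

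*SAP*

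**What the plan says.** **Interim.** SAP 14.1, repeated in the Protocol synopsis under Trial Stopping Rules, plans that "an interim analysis will also be performed when 75 patients completed Day 15 assessments for primary endpoint", and that "the following descriptive statistics efficacy analysis will also be presented". Item 5 of that list is the rate of mechanical ventilation, specified as "Patients who received Invasive/non-invasive Mechanical Ventilation by Day 15". Its scoring rule is that "if a patient did not experience mechanical ventilation by Day 15, he/she will be marked as a negative response". The sentence goes on to apply this even to patients ventilated after Day 15, and the SAP notes that the final analysis differs.

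**Final rate.** SAP 11.6.1 states: "Counts and percentages of patients for respiratory support at least once will be reported for each treatment arm". It covers five definitions of support. A Newcombe 95% CI and an uncorrected chi-squared p-value "will be computed between SOC and treatment arms A and B for patients with at least one respiratory support". One supplementary count is planned, of patients who required support; its condition is "If patients were eligible for respiratory support but did not receive one due to lack of resources". Death is not mentioned.

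**Time to support.** SAP 11.6.3 does mention death: "If a patient died before obtaining respirator support, the patient will be censored as a competing risk". Under SAP 11.3 such endpoints get a cumulative incidence display and a Fine-Gray model.

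**Death elsewhere.** SAP 11.1 carries death forward as WHO-7 category 7 and compares each category. SAP 11.9 compares mortality by Day 15, by Day 28 and overall.

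**The concern.** A yes/no ventilation variable has two ways of being no: the patient did not need ventilation, or the patient died first. The primary endpoint ranks the second as the worst possible outcome. The ventilation rate puts the two together.

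The rate of mechanical ventilation is a listed secondary endpoint (Protocol 3.2, SAP 2.3.2), and 11.6.1 attaches a p-value to it. If one arm has more deaths before ventilation, its rate falls for the wrong reason and the test can credit that arm with sparing patients ventilation. Phase 2b data are also to be used to select and rank the secondary endpoints for Phase 3 (Protocol 4.1, SAP 2.1), so a rate lowered by deaths could influence what is carried forward.

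**Working it through.** **Step 1. Apply the rules to three patients.** I take a patient who died before Day 15 as belonging to the interim set, because SAP 11.1 gives that patient a Day 15 score of 7.

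| Patient | Item 5 (14.1) | Rate (11.6.1) | WHO-7 at Day 15 |
|---|---|---|---|
| Ventilated by Day 15 | event | event | status that day |
| Discharged, never ventilated | non-event | non-event | 1 or 2 |
| Died on Day 5, never ventilated | non-event | non-event | 7 |

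The last two rows differ only in the final column.

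**Step 2. The plan's own figures.** The documents give no ventilation incidence and no power for this endpoint. The only powered figure is the pivotal 462 for the ordinal endpoint. With Table 2 averaged over arms (treatment column rescaled from 99.88% to 100%), N = 12(z0.975 + z0.90)² / [ln(1.75)² × (1 − Σp̄³)] = 461.0, so 462 reproduces. It does not bear on the ventilation rate. The relevant inputs from Table 2 are the Day 15 death rates, 2% SOC and 1.0% treatment.

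- Expected deaths per 50: 50 × 0.02 = 1.0 and 50 × 0.01 = 0.5.
- Expected deaths per 25 (75 patients at 1:1:1): 0.5 and 0.25.
- Suppose every death is unventilated and every such patient would otherwise have been ventilated. The SOC rate then drops 2 points and the treatment rate 1 point. The comparison shifts by 2 − 1 = 1 percentage point, in favour of SOC. A smaller unventilated share, equal in both arms, gives less.

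**Step 3. When it becomes material (assumed figures).** Two arms of 50 have equal underlying need, 10/50. In one arm, d of those 10 die unventilated; nobody else dies unventilated. That arm's rate is (10 − d)/50. Ventilated-or-died is (10 − d + d)/50 = 20% in both arms.

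| d | Rates | Difference (Newcombe 95% CI) | Chi-squared p | Ventilated or died |
|---|---|---|---|---|
| 2 | 16% vs 20% | −4 points (−19.1 to 11.3) | 0.60 | 20% vs 20% |
| 5 | 10% vs 20% | −10 points (−24.2 to 4.3) | 0.16 | 20% vs 20% |
| 8 | 4% vs 20% | −16 points (−29.4 to −3.1) | 0.014 | 20% vs 20% |

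At the interim, with 25 per arm, need 5/25 and d = 2, the rates are 3/25 = 12% against 20%.

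**Step 4. Deaths unrelated to need.** Use constant hazards, with a net ventilation risk of 20% by Day 15 and a net death risk F: hv = −ln(0.80)/15 and hd = −ln(1 − F)/15. The cumulative incidence of ventilation is hv/(hv + hd) × [1 − exp(−15(hv + hd))].

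| F | Ventilation incidence | Ventilated or died |
|---|---|---|
| 0% | 20.0% | 20.0% |
| 2% | 19.8% | 21.6% |
| 5% | 19.5% | 24.0% |
| 10% | 19.0% | 28.0% |
| 20% | 18.0% | 36.0% |

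The rate barely moves. The large effect in Step 3 requires deaths to fall on the patients who would have been ventilated.

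**Step 5. Whether another analysis repairs it.**

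- The quantity in Step 4 is the cumulative incidence that 11.6.3 displays and that the Fine-Gray model compares. It falls as deaths rise although the ventilation hazard is unchanged, so 11.6.3 shares the direction of the problem.
- SAP 11.3 drops a time-to-event endpoint if any patient had the event before randomization. Protocol 5.1 admits patients already on non-invasive ventilation, so that version may not be analysed at all.
- Ventilator-free days is an objective (SAP 2.2.2), but SAP section 11 defines no analysis of it.

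**The case against.** The strongest reply is that the item 5 rule is a Day 15 cut-off. Read in full, the sentence deals with ventilation that starts after Day 15; it never names death, and a negative response most naturally means no event. That stands: a reader might infer that the SAP declares death a success, and it does not. Scoring an unventilated death as a non-event follows from the wording in 14.1 and from silence in 11.6.1.

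Second, deaths are visible. WHO-7 status sits beside item 5 at the interim, and 11.1 and 11.9 carry their own comparisons. A careful reader would notice an excess of deaths. This lowers the risk of being misled, but the ventilation interval and p-value are unchanged.

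Third, item 5 is descriptive, with no test or decision rule, so a claim that it could drive an interim decision is not supported. The tested version is in 11.6.1.

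Fourth, the lack-of-resources count is a partial remedy. It would capture patients denied support who then died, but it is descriptive and does not reach other unventilated deaths.

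Fifth, ventilation incidence with death as a competing event is a legitimate quantity and a protocol endpoint. That is a good reason not to replace it. It is not a reason to let it stand alone as evidence of benefit.

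A reader might also set Table 2's 2% SOC deaths against its 1% on mechanical ventilation or ECMO and conclude that the ignored outcome is the larger one. The documents do not support this. Table 2 gives status on Day 15, not whether a patient was ever ventilated; item 5 also counts non-invasive ventilation; and some who die will have been ventilated and so are already events.

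**Conclusion.** The point holds as a statement about how the rate is scored and the direction in which it can mislead. Both ventilation rates treat an unventilated death as a non-event, the test in 11.6.1 can favour the arm with more such deaths, and nothing else in the SAP corrects that comparison.

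The size is conditional. At the planning death rates the expected distortion is at most about 1 percentage point, assuming the same share of deaths is unventilated in each arm. At those rates it would work against the active arms, so the planning figures do not suggest a bias towards ifenprodil. The distortion matters only if unventilated deaths are several per arm, unbalanced, and concentrated in patients who would otherwise have been ventilated. Reaching p = 0.014 in the example needed 8 of 10 such patients in one arm and none in the other. All need rates used here are assumptions.

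This is a cheap improvement, not a threat to the primary analysis.

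**What to change.** Keep the protocol's ventilation rate as it is. Add the following beside it in SAP 11.6 and 14.1 and in the mock shells:

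- **Interim:** the number and percentage with invasive mechanical ventilation, ECMO or death by Day 15, descriptive only.
- **Final:** the same composite by Day 29, each dose against SOC, with the Newcombe CI and chi-squared test already used in 11.6.1. For time to the composite, use a Cox model with the 11.3 covariates (age, site, treatment). Death is part of the event, so it is no longer a competing risk.
- **Components:** show ventilated patients and unventilated deaths on separate rows.
- **Interpretation:** state in advance that any claim of reduced ventilation will rest on the composite.

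State openly that the composite leaves out non-invasive ventilation, which item 5 includes, because Protocol 5.1 allows patients to enter the trial on it.

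The cost is one derived variable, extra table rows and a few sentences of SAP text; death and ventilation are already collected. The downside is that a composite mixes two outcomes of different weight, which is why the components should appear with it. Because the trial is open label, the text should be fixed before results by arm are reviewed.
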